#### Smoking Cessation

All participants who meet screening criteria at the baseline visit will come back and meet for a total of four sessions with a health educator to address smoking cessation. The study team will try to schedule the sessions as described here, but flexibility will be allowed for life circumstances, holidays, weather, etc. Sessions may be conducted over the phone or in person. In Session 1, about 1 week after the baseline visit but before the participant's "quit" date, the focus will be on preparing to quit and surviving the first days as a nonsmoker. Establishing quitting rituals, building support, and using the "Five A's" (Anticipate, Avoid, Alter, Alternatives, and Active) will be emphasized. Session 2, scheduled within 24 hours of the quit attempt, addresses maintaining motivation and coping with negative emotions and nicotine withdrawal. Session 3 will occur approximately one week postcessation. As in all sessions, problem solving and support building will be emphasized. In addition, dealing with negative cognitions will be addressed. In the final session, conducted three weeks postcessation, preventing relapse will be the emphasis. In a mailing prior to this session, participants are asked to do homework before the session that will facilitate making an individualized relapse prevention plan. Participants are asked to identify high-risk situations and difficulties encountered in previous cessation attempts and are walked through a series of suggestions in the event of a slip.

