At each session the participant will be asked to report their current smoking status, followed by an expired air carbon monoxide (CO) assessment. On the forth cessation visit if the participant fails the CO test (i.e., CO > 10 ppm), yet still claims to be abstinent from smoking, a salivary cotinine test will be given to provide a confirming/disconfirming assessment. Cotinine is a specific major metabolite of nicotine that can be detected in saliva for 45 to 80 hours. The procedure involves having the subject place a small cotton dental roll on his/her tongue for three minutes. At the end of this time, the subject expels the roll into a small vial. For those participants who fail the CO test but report using a nicotine replacement therapy (which would alter the results of the salivary cotinine test) will instead be tested for thiocyanate via blood draw. The amount of thiocyanate in a person's blood provides information about their level of exposure to cigarette smoke. Adverse events and concomitant medications will be reviewed at each session. Each of the 4 sessions will take approximately 1 hour to complete. If the session is completed over the phone, the physical assessments will not

be taken.

Next, there will be 4 follow-up phone calls. These calls are used to identify early relapse, encourage participants, and provide support. They also are used to review materials and information provided during the sessions with the health educator. The calls are made in the first few months of the intervention. Calls will take approximately 10-15 minutes each to complete.

Finally, participants receive six mailings over the course of the study. The first mailing, sent one week postcessation, provides information and a worksheet to facilitate relapse prevention. The next mailing, sent four weeks postcessation, focuses on coming off the patch. Nine weeks into the study, participants receive a mailing about stress management. The remaining three mailings are sent during months 7, 9, and 11. The topics covered include secondhand smoke, helping friends/family members to quit smoking, and a general review of some of cessation program items.

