#### Randomization

Following the smoking cessation sessions, all participants who are abstinent from smoking based on two-week prolonged abstinence criteria will come in for a randomization visit (Please note that in order to improve clarity, this visit is referred to as the Group Assignment Visit in the Participant Consent Form). The participant will be asked to report their current smoking status, followed by an expired air carbon monoxide (CO) assessment. For those who fail the CO test (i.e., CO > 10 ppm), yet still claim to be abstinent from smoking, a salivary cotinine test will be given to provide a confirming/disconfirming assessment. For those who fail the CO test but report using a nicotine replacement therapy (which would alter the results of the salivary cotinine test) will instead be tested for thiocyanate via blood draw. Participants who do not successfully quit smoking will be given a chance to recycle through the smoking cessation intervention a second time.

At this visit the study staff will perform an interval medical history with the participant, to ensure nothing critical has changed from the screening visit. Vitals will also be taken again (weight, pulse and blood pressure). Waist circumference will also be measured. Percentage of body fat will be measured using a bioelectrical impedance analysis. Inclusion/exclusion criteria will be reviewed again. Adverse events and concomitant medications will be reviewed. The participant will have an electrocardiogram (ECG) performed by study staff and reviewed by a physician for evidence of 2nd or 3rd degree AV block and to assess for previous silent myocardial infarction. If the ECG results are inconclusive, the participant will be advised to consult his/her primary care provider and will not be able to participate in the study. If the participant is still interested in participating in the study, he/she should contact his/her primary care provider in order to perform an exercise stress test. The test would be conducted under the supervision of the primary care provider. If the results of the exercise stress test indicate that it is safe for the individual to enroll in the study, and the primary care provider and the

study physician clear them for participation, then they will be allowed to enroll provided they meet other eligibility criteria.

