Although the primary analyses are for the randomized trial, the first phase of this investigation (open-label smoking cessation phase) will provide meaningful data regarding smoking cessation efforts for individuals. For this phase, the primary outcome will be prolonged tobacco abstinence at the final program session (session 4) defined as self-reported abstinence from all tobacco (not even a puff) for the last 14 days, confirmed by expired CO<10 ppm. The percentage of participants that discontinue the program prior to the 4th session will be summarized along with the reason for discontinuation. The overall abstinence rate at the end of the program will be summarized using a point estimate and 95% confidence interval, with subjects that discontinue study participation assumed to be smoking. In addition, logistic regression will be used to perform exploratory analyses to assess potential participant characteristics associated with abstinence at the end of treatment. Participant characteristics considered in this analysis will include: age (years), gender, smoking rate (cpd), and level of nicotine dependence (FTND).

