Although the primary analyses are for the randomized trial, the first phase of this investigation (open-label smoking cessation phase) will provide meaningful data regarding smoking cessation efforts for individuals. For this phase, the primary outcome will be prolonged tobacco abstinence at the final program session (session 4) defined as self-reported abstinence from all tobacco (not even a puff) for the last 14 days, confirmed by expired CO<10 ppm. The percentage of participants that discontinue the program prior to the 4th session will be summarized along with the reason for discontinuation. The overall abstinence rate at the end of the program will be summarized using a point estimate and 95% confidence interval, with subjects that discontinue study participation assumed to be smoking. In addition, logistic regression will be used to perform exploratory analyses to assess potential participant characteristics associated with abstinence at the end of treatment. Participant characteristics considered in this analysis will include: age (years), gender, smoking rate (cpd), and level of nicotine dependence (FTND).

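### The phase 1 abstinence outcome accepts only expired CO below 10 ppm at session 4, so participants cleared by the trial's own back-up test at that visit do not count as abstinent

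*SAP*

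**What the plan says.** **Outcome.** The SAP (Analyses for phase 1) sets the phase 1 primary outcome as "prolonged tobacco abstinence at the final program session (session 4"), based on 14 days of self-reported abstinence from all tobacco and "confirmed by expired CO<10 ppm". Protocol XI.1 has the same criterion: "for the last 14 days, confirmed by expired CO<10 ppm". Neither names another confirming test. The rate is to be reported with a 95% confidence interval, and an exploratory logistic regression looks for characteristics associated with abstinence. Participants who discontinue are taken to be smoking. No other missing-data rule is given for this phase.

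**Procedures at session 4.** Protocol VII.E.6 (Smoking Cessation) describes the fourth cessation visit. If CO is above 10 ppm and the participant still claims abstinence, "a salivary cotinine test will be given to provide a confirming/disconfirming assessment". A participant using nicotine replacement, which would distort cotinine, "will instead be tested for thiocyanate via blood draw". VII.E.6 (Randomization) repeats this sequence at the later randomization visit.

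**Mode of contact.** The same section states: "Sessions may be conducted over the phone or in person". Session 4 is not excepted. It then says: "If the session is completed over the phone, the physical assessments will not" be taken.

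**The concern.** The protocol recognises that a CO reading can be too high in someone who is not smoking, and it provides a second test at this visit to settle the matter. The analysis definition ignores that test's result. A participant can therefore be verified as abstinent at session 4, pass to randomization, and still be a non-abstainer in the phase 1 analysis.

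The thiocyanate route is a realistic one. Session 4 is held three weeks after quitting and the patch course lasts six weeks, so a patch user who is on schedule is still using nicotine replacement then.

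Two gaps lie beside this. A phone session 4 yields no CO, so the definition cannot be met there, and the discontinuation rule does not cover someone who took part in the session. And the outcome needs CO below 10 ppm while the back-up test is prompted only above 10 ppm, so a reading of exactly 10 neither confirms abstinence nor leads to a second test.

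At stake are the phase 1 abstinence rate, its confidence interval and the classification of the outcome in the exploratory regression.

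**Working it through.** **1. Stated rule against procedure, by what happens at session 4** (each participant reports 14 days of abstinence)

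| Session 4 finding | Trial procedure | Phase 1 outcome as written |
|---|---|---|
| CO below 10 ppm | Passes | Abstinent |
| CO exactly 10 ppm | Not a failure, no back-up test | Not abstinent |
| CO above 10 ppm, cleared by cotinine or thiocyanate | Confirmed abstinent | Not abstinent |
| CO above 10 ppm, not cleared | Not abstinent | Not abstinent |
| Phone session, no CO | Unverified until the randomization visit | Cannot be met; no rule stated |

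Rows two, three and five are where the definition and the procedures part. In row three the protocol itself has verified abstinence at the stated time point.

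**2. The plan's own figure.** Protocol XI.2 (Anticipated Attrition) expects 1267 enrolled and 45% abstinent at the end of the cessation phase: 1267 × 0.45 = 570.15, which reproduces the stated 570. The onward flow also reproduces: 570 − 57 − 78 = 435, or 145 per group.

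**3. Size under an assumption.** The documents do not say what share *f* of true quitters would lack a session-4 CO below 10 ppm. I assume 1% to 20%, covering back-up confirmations and phone sessions together, and assume that all of them are counted as not abstinent. The reported rate is 570 × (1 − *f*) / 1267, with interval *p* ± 1.96 × √(*p*(1 − *p*)/1267).

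| Assumed *f* | Counted abstinent | Reported rate | 95% CI |
|---|---|---|---|
| 0 | 570 | 45.0% | 42.2 to 47.7 |
| 1% | 564 | 44.5% | 41.8 to 47.3 |
| 2% | 559 | 44.1% | 41.4 to 46.9 |
| 5% | 542 | 42.8% | 40.1 to 45.5 |
| 10% | 513 | 40.5% | 37.8 to 43.2 |
| 20% | 456 | 36.0% | 33.3 to 38.6 |

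Wilson intervals agree to within 0.1 point.

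**4. When the shift matters.** The planned half-width is 1.96 × √(0.45 × 0.55/1267) = 2.7 points. The shift is 45 × *f* points, so it exceeds the half-width once *f* is above 2.74/45 = 6.1%. For Iowa's 500 participants the half-width is 4.4 points and the threshold is 4.36/45 = 9.7%.

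**5. Why the phone gap is separate.** Suppose 10% of all participants have a phone session 4 and abstinence does not depend on mode. Counting the phone quitters as not abstinent gives 513/1267 = 40.5%. Dropping phone participants from the denominator gives 513/(0.9 × 1267) = 513/1140 = 45.0%. The plan does not say which to do.

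**The case against.** The strongest reply has four parts.

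**The definition is conservative, and the analysis section may only abbreviate.** Requiring biochemical confirmation at a fixed time is a legitimate choice, and the authors may have taken the back-up test as understood. This carries weight for phone participants, who have no test at session 4. It does not answer the case of those cleared by cotinine or thiocyanate, who are confirmed at that very visit. If abbreviation was intended, one clause settles it.

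**The plan does not count phone participants as smokers.** A reader might infer that it does. The documents do not support this: the smoking assumption applies to those who discontinue, and someone who takes part by phone has not. Their status is undefined, and they are not verified quitters at session 4 either.

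**The phase 1 count need not equal the number entering randomization.** A reader might take any mismatch as an error, or say that the outcome contradicts the eligibility rule. Entry is decided at a separate, later visit. Participants who fail may repeat the program once (VII.E.6), and people who quit on their own skip the cessation phase (VI.13). The counts can differ under any definition, so a mismatch is not evidence of a fault.

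**The logistic model is not shown to be biased in a given direction.** A lower event rate does not by itself push coefficients down. That depends on whether lacking a qualifying CO is related to age, gender, smoking rate or dependence, on which the documents are silent. What stands is that the outcome is misclassified.

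**Conclusion.** The point holds as a minor defect of definition. Applied as written, the phase 1 outcome classes as non-abstinent some participants whom the protocol's own session-4 back-up test confirms as abstinent, so it understates the rate. The phone-session gap and the reading of exactly 10 ppm are real omissions; the latter may be no more than a slip in the inequality sign.

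The size is unknown. The 44.5% to 36.0% range rests on an assumed 1% to 20% of quitters, pools both routes, and takes every affected person as counted non-abstinent, which for phone sessions the plan does not state. At the low end the effect is negligible. A statement that the true rate would fall outside the reported interval is conditional on an affected share that the documents do not give.

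The effect is confined to the single-group phase 1 rate, its interval and the exploratory regression. The randomized comparison and the 145 per group do not depend on it.

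**What to change.** - **Outcome.** In the SAP and protocol XI.1, define phase 1 abstinence as 14-day self-report confirmed at session 4 by CO or, when CO fails, by the cotinine or thiocyanate result from that visit.
- **Cut-off.** Use one CO threshold in VII.E.6, XI.1 and the SAP, and state how a reading of exactly 10 ppm is classed. No back-up test was called for at that reading.
- **Phone session 4 without CO.** Treat as not confirmed in the main estimate. Add a sensitivity analysis that uses verification at the randomization visit.
- **Transparency.** Report the CO-only rate alongside. Data collection is complete (protocol I.4 and VII.A.4), and admitting the back-up test can only add abstainers, so readers should see both figures. Give the numbers confirmed by each route and the number of phone sessions, which would replace the assumed range with a count.

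The cost is a few sentences and one more reported rate. No new data are needed, since the protocol already called for these tests. In the sensitivity analysis, verification comes later for phone participants, and someone abstinent at session 4 who smoked before the randomization visit would be misclassified. That is why it should not be the main estimate.

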As noted above, when the application for the current study was originally submitted, it was intended to be conducted at the University of Memphis. At that time, the study called for recruiting a majority of African American participants. Given the demographic composition of both Rochester, MN and Iowa City, IA, however, this was no longer feasible. Consequently, the recruitment goals for the study were modified accordingly and with the approval of NHLBI. The subsequent relocation of [name] to the University of Tennessee Health Sciences Center in Memphis, TN, which is a more demographically diverse area, has increased opportunities for minority recruitment for the multi-site trial. [name] has a long history of successful recruitment of minority participants for clinical trials during the 20 years that he was on faculty at the University of Memphis. The Memphis, TN site will therefore assist with efforts to recruit African American participants into the trial.

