As noted above, several of the original exclusion criteria were subsequently removed following consultation with our physician investigators as well as the Protocol Review Committee. In the current protocol, a known contraindication or sensitivity to nicotine replacement therapy (NRT) is no longer an absolute exclusionary factor. Instead, individuals who are not able or willing to use NRT will be given the option of receiving the behavioral portion of the smoking cessation program without NRT. Similarly, we consulted a dermatologist at Mayo who informed us that it was not necessary to exclude patients with a history of atopic or eczematous dermatitis or dermatosis from participation in the study or from receiving transdermal nicotine. In the event that these individual are unable to tolerate the nicotine patch, they will still be given the option of receiving only the behavioral portion of the smoking cessation intervention. Insulin-dependent diabetes mellitus, fasting blood sugar of > 160 mg/dl, anemia (as measured by hemoglobin < 11g/dl), and history of a serious illness that might limit longevity also are no longer exclusionary, as it was felt that individuals meeting these criteria would not be placed at significantly increased risk by participating in the study, and might receive potentially important benefits. Exclusion criteria related to a body mass index (BMI) of > 21 kg/m^2 and unexplained weight loss of more than 10 pounds in the past year also were determined unnecessary by the physician investigators. Finally, the original protocol included an exclusion criterion related to the inability to collect 24-hour urine measures with a volume of > 500 ml. However, because 24-hour urine samples are no longer being collected (they have been replaced by overnight measures of urinary chloride excretion), this exclusion criterion is no longer necessary.

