#### D. Collaborating Sites

This study is a multi-site clinical trial also being conducted at the University of Tennessee Health Sciences Center in Memphis, TN, and at the Mayo Clinic in Rochester, Minnesota. All three sites are utilizing the same protocol. The Memphis, TN site is being funded by a separate grant from the National Heart, Lung, and Blood Institute. The Rochester site is being funded by the same grant that is funding the Iowa City, IA site (NHLBI grant number HL72782, [name], PI). Mayo Clinic Rochester was the PI's ([name]) institution prior to relocating to Iowa City. During the remainder of the study in Rochester, [name]. will serve as the site-PI for the study at the Mayo Clinic. He will also serve as a co-investigator for the overall parent study.

1.7 *Literature cited / references (if attaching a grant or protocol enter N/A).*  
See Attached.

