## **XI.2**

### ***Provide the rationale or power analysis to support the number of subjects proposed to complete this study.***

This study is a multi-site, randomized clinical trial, with study sites in Iowa City, IA, Rochester, MN, and Memphis, TN. The sample size calculations provided below reflect the target number of participants for the entire trial, across each of the three sites. Only subjects that meet criteria for tobacco abstinence at the end of the 4-week smoking cessation phase will be eligible for randomization, and of these participants, only those that meet criteria for prolonged abstinence through 1-year follow-up will be included in the primary analysis. Because methodological factors such as abstinence criteria and length of follow-up can have a significant impact on the primary endpoints, we consulted the extant literature and chose only studies that were fairly similar to the proposed project to obtain estimates for sample-size planning. The majority of these studies present data as change from baseline. For this reason, sample-size calculations for the present investigation are based on an analysis of change scores. However, an alternative to analyzing change scores is to analyze follow-up data using an analysis of covariance model with the baseline value included as a covariate. In addition to adjusting each subject's follow-up score for his or her baseline score, the analysis of covariance approach has the advantage of being unaffected by baseline differences. This approach also typically has greater statistical power to detect a treatment effect than analyzing change scores (Vickers et al. 2001). Therefore, sample-size requirements based on an analysis of change scores will provide similar or greater statistical power for analyses that are performed using an ANCOVA approach.

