Data Analytic Plan

Study Title: Blood Pressure Control in Hypertensive Smokers

NCT: NCT00113074

Approval Date: 09/20/2021

Treatment and Prevention Study Data Analytic Plan

Overview:

The main statistical analyses will be for the three-group randomized clinical trial with the primary analyses restricted to participants that do not relapse to smoking. Participants who discontinue study participation will be assumed to have relapsed to smoking. Therefore, analyses will be restricted to those with available data.

The primary efficacy endpoints are BP and body weight. Since the aim is to evaluate long-term efficacy, the primary analysis will evaluate treatment effects at 1-year. Analyses will also be conducted to assess changes in BP and body weight at six months. The primary analysis will be restricted to participants that have not relapsed to smoking and who provide follow-up data. Secondary analysis will be performed using all participants. The primary analysis will be performed using ANCOVA to assess for treatment effects adjusting for the baseline value of the dependent variable, study site, and any baseline variables found to differ significantly between groups. In all cases, each of the two experimental groups will be compared to the UL group. Since there are two pair-wise treatment comparisons of interest (BPC vs. UL; WGP vs. UL), we will utilize Fisher's least significant difference (LSD) approach to protect against inflation of the experimentwise error rate. An initial omnibus test will be used to test the null hypotheses that all group means are equal. Rejection of the null hypothesis will result in subsequent pair-wise comparisons between treatment groups. Conversely, if the null hypothesis associated with the omnibus test is not rejected, pair-wise comparisons will not be necessary.

Secondary endpoints will include servings of fruits and vegetables per day, dietary fat intake (% of total energy from fat), overnight urinary chloride excretion (mmol/day), and self-reported physical activity (kcal/kg/day). The analyses for the secondary endpoints will be similar to that for the primary endpoints, with groups compared using ANCOVA to assess for treatment effects adjusting for baseline values, study site, and baseline variables found to differ significantly between groups. In all cases, each of the two experimental groups will be compared to the UL group.

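### The exploratory phase 1 model of who quits omits study site, so if data from several sites are pooled, site differences could be reported as effects of a listed characteristic

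*SAP*

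**What the plan says.** The SAP section on analyses for phase 1, repeated in Protocol XI.1, states that "logistic regression will be used to perform exploratory analyses to assess potential participant characteristics associated with abstinence at the end of treatment". The covariate list is: "Participant characteristics considered in this analysis will include: age (years), gender, smoking rate (cpd), and level of nicotine dependence (FTND"). Site is not named. The main phase 1 result is also unstratified: "The overall abstinence rate at the end of the program will be summarized using a point estimate and 95% confidence interval".

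In the randomized phase, the SAP Overview specifies ANCOVA "adjusting for the baseline value of the dependent variable, study site, and any baseline variables found to differ significantly between groups" for the primary endpoints, and adjusts the secondary endpoints for site as well.

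Protocol XI.2 describes a multi-site trial "with study sites in Iowa City, IA, Rochester, MN, and Memphis, TN". Its Anticipated Attrition text expects 1267 enrolled across the sites, 500 of them in Iowa City, with 45% (570) abstinent at the end of the cessation phase. Protocol C.1 says of Memphis that it is a place "which is a more demographically diverse area, has increased opportunities for minority recruitment for the multi-site trial". Protocol D adds: "All three sites are utilizing the same protocol".

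**The concern.** In the ANCOVAs, treatment groups are randomized, so site adjustment mainly gains precision. In phase 1 nothing is randomized: age, gender, cpd and FTND are simply what participants bring, and site can be related both to them and to quitting. Site is therefore a possible confounder in the one model that leaves it out while asking which participants quit.

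The documents make site differences plausible. Demographics differ by site (Protocol C.1) and race is not in the model. Recruitment periods differ: Rochester recruited through December 2006, while this application gives December 1, 2007 as its start date. Cessation sessions may be held by phone, without physical assessments (Protocol VII.E.6), yet the phase 1 outcome needs CO confirmation, so measured abstinence could vary with local practice.

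At stake is the reading of the exploratory results. A characteristic unrelated to quitting within any site could be reported as a predictor, or a real association could be exaggerated or diluted.

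**Working it through.** **The plan's own flow.** 1267 × 0.45 = 570 abstinent; less 57 (10%) and 78 (stated as 15%) leaves 435. The flow reproduces: 15% of 513 is 76.95, a rounding difference. No power or effect size is stated for the phase 1 model.

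**Inputs.** From Protocol XI.2: n = 1267, overall abstinence 45%, Iowa 500/1267 = 39.5%. Assumed, because the documents do not give them: site shares 40/20/40%, within-site cpd SD 8, other covariates unrelated to site and cpd, and these site values:

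| Scenario | Abstinence by site | Mean cpd by site |
|---|---|---|
| A | 40/45/50% | 20/18/16 |
| B | 35/45/55% | 20/18/16 |
| C | 35/45/55% | 22/19/16 |

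Each averages 45% overall.

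**Distortion with no true cpd effect within site.** Approximate log odds per cpd = (between-site covariance of cpd and logit abstinence) / (between-site + within-site variance of cpd). The middle site sits at the mean cpd and drops out of the covariance.

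- A: 0.4 × 2 × (logit 0.40 − logit 0.50) = 0.8 × (−0.405) = −0.324. Variance 3.2 + 64 = 67.2. Slope −0.00483 per cpd; OR per 10 cpd = exp(−0.0483) = 0.95.
- B: 0.8 × (−0.619 − 0.201) = −0.656; −0.656/67.2 = −0.00976; OR 0.91.
- C: 1.2 × (−0.820) = −0.984. Variance 7.2 + 64 = 71.2; slope −0.0138; OR 0.87.

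**False-positive rate at two-sided 0.05.** SE per 10 cpd ≈ 10/(√(1267 × 0.45 × 0.55) × SD of cpd). This is 10/(17.7 × 8.20) = 0.0689 for A and B, and 10/(17.7 × 8.44) = 0.0669 for C. The ratios to SE are 0.70, 1.42 and 2.07. Then 1 − Φ(1.96 − z) + Φ(−1.96 − z) gives about 11%, 29% and 54%.

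Simulated logistic fits at n = 1267 agree:

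| Scenario | Without site | With site |
|---|---|---|
| A | 10–12% | 4–6% |
| B | 27–31% | 5–6% |
| C | 53–56% | 5–6% |

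With 800 replicates the standard error at 53% is √(0.53 × 0.47/800) = 1.8 points, so the ranges are mostly simulation noise.

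**Distortion of a true within-site OR of 0.80 per 10 cpd.** Multiplying by the distortion gives 0.80 × 0.953 = 0.76, 0.80 × 0.907 = 0.73 and 0.80 × 0.871 = 0.70. Reversing the site ordering means dividing: 0.84, 0.88 and 0.92. Large-sample fits agree. The ranges extend to 0.77 and 0.95 if each site's abstinence rate is fixed at that site's mean cpd. With site in the model the fits return 0.79 to 0.80.

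**Sensitivity.** A second simulated grid used all four listed covariates, sites of 500/384/383 and cpd SD 9, with no true cpd effect:

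| Abstinence gap (points) | cpd gap | Without site | With site |
|---|---|---|---|
| 10 | 3 | 6.6% | 5.8% |
| 10 | 6 | 9.8% | 3.4% |
| 20 | 3 | 11.0% | 7.4% |
| 20 | 6 | 31.2% | 3.8% |
| 30 | 3 | 23.6% | 5.0% |
| 30 | 6 | 56.0% | 4.8% |

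Where either gap was zero, the rate without site was 3.6% to 6.0%, that is, nominal.

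**Affordability.** Four terms on 570 expected abstainers is 570/4 = 142.5 events per term; with two site indicators it is 570/6 = 95.

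**The case against.** The strongest reply is that this model is labelled exploratory, carries no hypothesis or power, and lists characteristics to be considered without closing the specification. That stands and limits the weight of the point. It does not remove the confounding, and a site term added later would be an unplanned choice.

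Nor is site in the exploratory Cox model or the rank-sum, Fisher and Kruskal-Wallis comparisons, so its absence here fits the plan's pattern outside ANCOVA. That is fair, but those analyses compare randomized groups; this one does not.

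Four stronger readings are tempting, and the documents do not support them:

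- **That site is a confounder.** Protocol C.1 supports demographic differences only. There are no site figures for cpd, FTND, age, gender or abstinence, and Protocol C.1 and D describe a common protocol, cross-site training and regular calls.
- **That phase 1 is certainly pooled.** Protocol I.4 and VII.E.6 refer to Iowa enrollment and 500 smokers, while XI.2 describes three sites and 1267. The phase 1 text does not state its scope. If only Iowa is analyzed, the point falls away.
- **That a real association could vanish.** Under the assumptions above it is attenuated to 0.84 to 0.95, not erased.
- **That patch use should be adjusted for too.** Use during treatment is post-baseline and partly depends on the outcome, because Protocol VII.E.6 stops the patch in participants who repeatedly smoke while wearing it. Initial dose is set from cpd, so adjusting for dose would absorb part of the cpd association.

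**Conclusion.** The omission is real and inconsistent with the site-adjusted ANCOVAs, but its consequence is conditional. It needs pooled data and sites that differ in both abstinence and a listed characteristic. Under the assumed gaps of 10 to 20 points and 4 to 6 cpd, the distortion of a null odds ratio is modest (0.87 to 0.95 per 10 cpd), but at n = 1267 that is enough to raise the false-positive rate to between about 10% and 56%. With smaller gaps it is close to nominal. No result in the documents shows which case applies.

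A reader might infer that the blood pressure and weight conclusions are at risk. They are not: this model plays no part in them. The point is a minor improvement.

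**What to change.** In the SAP phase 1 section and Protocol XI.1, state which sites the analysis covers. When data from more than one site are pooled, include study site as a fixed effect in the logistic model alongside age, gender, cpd and FTND, and report abstinence by site next to the overall rate.

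Do not adjust for patch use during treatment or for patch dose. At most, describe abstinence by whether NRT was accepted or the behavioral program alone was chosen at the start.

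The cost is a sentence or two of text and two degrees of freedom on about 570 expected abstainers. No new data are needed, and since Protocol I.4 says that only analysis and manuscript preparation remain, the change can still be made.
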